 - ii. If there has been less than one week between the last intake of study drug and EoS visit, participant will be asked to attend to a Safety-follow up visit, two weeks after the last intake of study drug, to perform safety assessments only.
 - c. *Non-completers who discontinue the study because they withdraw their consent*: Participants that received at least one dose of study treatment, but prematurely discontinued from the study before completion of Visit 9 due to withdrawal of informed consent. These participants, if possible, will be asked to attend to an EoS Visit.
 - i. The visit must be scheduled as soon as possible after withdrawal.
 - ii. If the participant withdraws consent during a visit but agrees to complete the visit, then, the investigator will complete an EoS Visit. All the data collected up to and including this visit will be used in the analysis.
 - iii. If the participant withdraws consent and refuses to complete the EoS Visit, no new information will be collected. However, it is recommended, outside the scope of this study, to perform a safety assessment within 2 weeks after treatment discontinuation.
- (3) Informed consent at the Screening visit must be obtained before any study specific procedure.
- (4) Participant eligibility should be documented in a Participant Eligibility Form and submitted to the study medical monitor immediately after Visit 1 for approval before Visit 2.
- (5) Not applicable for non-completers (i.e.: participants who received at least one dose of study treatment but prematurely discontinue the study before its completion).
- (6) The full State-Trait Anxiety Inventory (STAI) (Forms Y-1 & Y-2) will only be administered at Screening (Visit 1), Baseline (Visit 2) and Visit 8/EoS, whereas Form Y-1 ("state" anxiety) will be administered at all other visits.
- (7) The number of visits to healthcare services outside of the trial (primary care, mental health services & ER visits) will be evaluated 'in the last month' at Baseline and at V4, V6 and V8/EoS.
- (8) Vital signs and electrocardiogram (ECG) should be obtained for a participant in the same manner throughout the study (e.g., obtained from the same arm).

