2. STUDY OBJECTIVES AND ENDPOINTS

2.1. Study Objectives

Primary Objectives

- To investigate the efficacy of vafidemstat in the treatment of agitation and aggression in adult BPD patients
- To investigate the efficacy of vafidemstat in the treatment of adult BPD patients

Secondary Objectives

- To investigate the effect of vafidemstat in reducing the severity of BPD symptoms in adult patients
- To evaluate the safety of vafidemstat in adult BPD patients

Exploratory Objectives

- To explore the impact of vafidemstat on functional impairment in adult BPD patients
- To explore the impact of vafidemstat on cognition in adult BPD patients
- To evaluate vafidemstat plasma concentrations (pharmacokinetics) as well as vafidemstat's LSD1-target engagement in peripheral blood mononuclear cells (PBMCs) (pharmacodynamics) after treatment

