All enrolled participants will need to maintain their pre-screening psychotherapy schedule throughout the trial duration, given that psychotherapy is the standard of care for BPD. Participants entering the study cannot start any type of psychotherapy within 3 months prior to enrollment or throughout the trial duration. Specifically, participants receiving psychotherapy before initiating the study need to remain in psychotherapy throughout the trial. However, those participants not receiving psychotherapy before the study should not initiate psychotherapy during the trial. Participants deemed needing immediate or emergent psychotherapy and those initiating psychotherapy during the study will be discontinued from the trial.

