5.3.3 Visit to Health Care Services

The number of visits to primary care services, mental health services, emergency room services and the overall number of visits to any health care services in the month prior to the Visit will be summarized descriptively by Visit and treatment.

In addition, the number and frequency of patients for each reason of visit will be summarized. For post-baseline Visits, the change from baseline for the number of visits by type of service and reason will be calculated and included in the summary. The number and frequency of patients having visited health care services at least once will also be summarized by visit, type of service and reason for visit.

The total number of visits by type of services will be calculated for each patient across all Study Visits. As an exploratory analysis only, the Mann-Whitney test will be used to compare the total number between the two treatment arms. Only patients who do not discontinue early will be included in this analysis.

A listing by patient will be produced showing the number of visits and the reason for the visits.

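### The exploratory test of healthcare visits totals all study visits, so it includes the pre-treatment month, leaves V9 unresolved and omits early discontinuers

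*SAP*

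**What the plan says.** SAP 5.3.3 covers visits to healthcare services in two parts.

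The first part is descriptive. Counts "in the month prior to the Visit will be summarized descriptively by Visit and treatment", and "For post-baseline Visits, the change from baseline for the number of visits by type of service and reason will be calculated". The section also summarizes the number of patients with at least one visit.

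The second part is the only between-arm test that the SAP specifies for this endpoint. Its outcome is a sum: "The total number of visits by type of services will be calculated for each patient across all Study Visits". The test is then named: "As an exploratory analysis only, the Mann-Whitney test will be used to compare the total number between the two treatment arms". Its population is restricted: "Only patients who do not discontinue early will be included in this analysis".

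On collection, footnote 7 to Protocol Table 1 sets a one-month recall "at Baseline and at V4, V6 and V8/EoS". Protocol 7.2.10 names the same four visits for that recall. Table 1 in the protocol, and its copy in SAP 7.1, also mark the item at V9, but with footnote 5 (not applicable to non-completers) and not footnote 7. The activity list for V9 in Protocol 7.7.9 does not contain the item.

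**The concern.** A total used to compare arms should contain time during which the arms differ in treatment. The sum in SAP 5.3.3 has no restriction to post-baseline visits, although the change-from-baseline summary in the same section does. SAP 3.2 defines the endpoint as the difference from baseline to Weeks 8-12 and the change over time. A sum that contains the Baseline report is neither.

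Three features of the rule matter:

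- The Baseline report describes a month that treatment cannot affect.
- V9 may or may not enter the sum. If it enters with a one-month recall, it repeats part of the V8 report and adds weeks in which, by Protocol 5.1.1, everyone takes placebo.
- Dropping early discontinuers selects on an event after randomization. Some withdrawal reasons are plausibly linked to service use. Protocol 3.1 says: "Participants deemed needing immediate or emergent psychotherapy and those initiating psychotherapy during the study will be discontinued from the trial". Protocol 4.2 lists a suicide attempt or significant suicide risk. Table 1 (footnote 2) asks participants who stop early to complete the V8/EoS assessments, which include this item. The data are therefore to be collected, but the test does not use them.

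At stake is the sensitivity and interpretability of one exploratory comparison.

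**Working it through.** **Planned numbers (SAP 4.7).** With effect size 0.51, two-sided alpha 0.025 and 80% power, n per arm = 2(2.241 + 0.842)² / 0.51² = 73.1, so 74. The t-based calculation gives 74.4, so 75, as stated; power at 75 per arm is 0.811. With 20% dropout, 75 / 0.8 = 93.75, so 94 per arm and 188 in total. The plan's figures reproduce. The test in 5.3.3 would leave out 188 − 150 = 38 participants, and 38 / 188 = 20.2%. The plan states no figure for the healthcare-visit test itself.

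**Recall windows.** Scheduled days are 1 (Baseline), 29 (V4), 57 (V6), 85 (V8) and 99 (V9). With a 28-day month:

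- Baseline covers Days −27 to 1, before treatment.
- V4, V6 and V8 cover Days 1-29, 29-57 and 57-85, with no overlap.
- V9, if collected with the same recall, covers Days 71-99. Days 71-85 are already in V8, so 14 days count twice. Days 85-99 are the placebo run-out.

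For shifts a at V8 and b at V9 within ±2 days, the overlap is 28 − (14 + b − a), which runs from 10 to 18 days. With the SAP's 30.417-day month (SAP 4.2) the V8-V9 overlap is 16.4 days (12.4 to 20.4), and about 2.4 days overlap at each earlier pair of visits.

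**Dilution of the ratio of means.** Assume a constant background rate of 1 per month, rate ratio r on drug, and a return to the background rate in the run-out.

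- V4 + V6 + V8: 3r / 3 = r.
- Adding Baseline: (1 + 3r) / 4. For r = 0.70 this is 0.775, a 22.5% reduction. For r = 0.50 it is 0.625, a 37.5% reduction.
- Adding Baseline and V9 with one-month recall: (1 + 3r + 0.5r + 0.5) / 5. For r = 0.70 this is 0.79, and for r = 0.50 it is 0.65.

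**Effect on the rank test.** A Mann-Whitney test does not estimate a ratio of means, so power was simulated: gamma-Poisson counts, 75 per arm, two-sided 5%, 3,000 runs per scenario. Background rates of 1 and 3 visits per month and gamma shapes of 1 and 3 are assumptions, because the documents give none. The ranges run over those scenarios.

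| True ratio | V4+V6+V8 | plus Baseline | plus Baseline and V9 |
|---|---|---|---|
| 0.70 | 35-85% | 20-60% | 18-53% |
| 0.50 | 85-100% | 57-99% | 51-96% |

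**Direction.** Under randomization the Baseline month has the same expected count in both arms. It adds noise and shrinks the contrast, but does not bias the test when there is no effect.

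**The case against.** The strongest reply is that this is one test, labelled exploratory, outside the Hochberg success rule (SAP 4.12) and the interim decision (SAP 4.8). The by-visit summaries, changes from baseline and proportions with any visit do not add the pre-treatment month to on-treatment counts and state no completer restriction. All of this stands, and it limits the consequence.

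A completer restriction also has a rationale: an unadjusted rank test on totals needs equal observation time. That is fair, but an offset achieves the same without discarding people.

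Four stronger readings are tempting, and the documents do not support them.

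- A reader might infer that service use is the only measure behind the objective "To explore the impact of vafidemstat on functional impairment in adult BPD patients", so that the objective cannot be answered. No section maps that objective to an endpoint. Protocol 1.4.2 groups BPDCL, a primary endpoint here, with measures of functioning used in the Phase IIa study. What can be said is that no dedicated functioning scale is listed.
- A reader might treat the V9 double count as certain. Footnote 7 and the recall visits named in Protocol 7.2.10 do not include V9, and Protocol 7.7.9 omits the item. The V9 overlap is conditional; the inconsistency is not.
- A reader might conclude that the participants whose service use rose are removed. Protocol 4.2 lists many withdrawal reasons, and no document gives the share linked to service use. Some excluded participants may be of this kind.
- A reader might call the Baseline month a source of bias. It dilutes the comparison.

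A simple sum over V4, V6 and V8/EoS would also create a new problem once discontinuers are included. Their EoS visit comes soon after withdrawal. Stopping near week 10 gives a recall of about weeks 6-10, which overlaps V6 (weeks 4-8). Stopping near week 2 brings in about two pre-treatment weeks. The fix has to deal with this.

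**Conclusion.** The point holds for the one Mann-Whitney test in SAP 5.3.3. As written, its total includes a pre-treatment month, and its population excludes about 38 of 188 randomized participants at the planned dropout. The Baseline month turns a true 30% reduction into 22.5% and a true 50% into 37.5%, given a constant background rate. The size of the power loss depends on assumed rates and dispersion. The direction of any effect from excluding discontinuers cannot be determined from the documents. The V9 overlap of about 14 days (10-18 with visit windows) arises only if V9 is collected with a one-month recall. No primary or secondary conclusion is affected. The correction is nevertheless worth making, because it is cheap and concerns the only between-arm test specified for this listed endpoint.

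**What to change.** In SAP 5.3.3:

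- Define the total as the on-treatment reports V4 + V6 + V8/EoS, excluding Baseline and V9.
- Use the Baseline count as a covariate.
- Include all FAS participants with at least one post-baseline report, with the log of time covered as an offset, for example in a negative binomial model.
- For early EoS visits, count only on-treatment days not already covered by an earlier report. Apply this to the offset and, where visit dates allow, to the count.
- Keep the completer Mann-Whitney test, on the corrected total, as supportive.

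Reconcile the V9 mark in Table 1 (protocol and SAP) with footnote 7 and with Protocol 7.2.10 and 7.7.9. If V9 is collected, state its recall period and report it separately.

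The cost is SAP and schedule wording plus minor programming, with no new data. The small downside is a model assumption in place of a purely rank-based comparison, and the retained rank test offers a check on it.

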5.3.4 Exploratory Assessments

The analysis of C-SSRS is described in Section 5.2.10, the analysis of visits to Health Care Services in Section 5.3.3 and the PK/PD analysis in Sections 5.3.1 and 5.3.2.

The Agitation-Aggression Psychiatric Inventory-Clinician Report (AAPI-CR) and Brief Assessment of Cognition (BAC) Scale results will be primarily analyzed using the following variables.

- AAPI-CR: Total Score, Agitation/Aggression Subscale and Psychiatric Subscale
- BAC: Standard-Composite TScore

Those variables will be listed and summarized descriptively by Visit and Time Point using the FAS. Additional listings will be produced with the results for each item.

5.4 COVID-19 Related Considerations

The impact of Covid-19 on the study will be investigated as follows:

- Covid-19 related discontinuations will be displayed in the disposition summary as a reason for discontinuation
- Number and frequency of Covid-19 related adverse events (i.e., infection) will be displayed on the main summary table for adverse events
- Number and frequency of concomitant medication for Covid-19 will be displayed on the main summary table for concomitant medication
- Covid-19 related protocol deviations will be summarized in an additional summary table
- For the primary efficacy analysis, patients who discontinue/could not complete the assessment due to Covid-19 will not be given special consideration and treated the same as any other patients with other reasons for missing data

5.5 Changes in the Conduct of the Study or Planned Analysis

There are no changes in the planned analysis compared to the study protocol.

7.1 Schedule of Assessments

Table 1. Schedule of Assessments and Procedures

Study Procedures	Visit	V1 (Screening)	V2 (Baseline)	V3	V4	V5	V6	V7	V8 / EoS ⁽²⁾	V9 Run-out (Safety F-up) ⁽¹³⁾
	Week	-1	0	2	4	6	8	10	12	14
	Day ⁽¹⁾	-7 to 1	(-5 to 1) ±5	15±2	29±2	43±2	57±2	71±2	85±2	99±2
Informed Consent Form ⁽³⁾		X								
Inclusion/Exclusion Criteria		X	X							
Mini-International Neuropsychiatric Interview (MINI)		X								
Demographics		X								
Medical history		X								
Prior and concomitant medication		X	X	X	X	X	X	X	X	X
Physical examination (height –only at V1- and weight)		X	X	X	X	X	X	X	X	X
Tuberculosis status by medical history, signs and symptoms		X								
Urine pregnancy test (females of reproductive age)		X	X						X	
Urine drug screening		X	X	X	X	X	X	X	X	X
Subject Eligibility Form		X ⁽⁴⁾								
Randomization			X							
Follow-up phone calls (only applicable if subject is receiving concomitant antidepressants) ⁽¹²⁾		At V2 (Baseline): after 6-8h; 24h; and 48 h, after first drug administration								
Rating Scales/Clinical Outcomes Assessments (COAs)										
Columbia-Suicide Severity Rating Scale (C-SSRS)		X	X	X	X	X	X	X	X	X ⁽⁵⁾
Agitation-Aggression Psychiatric Inventory-Clinician Report (AAPI-CR)		X	X		X		X		X	X ⁽⁵⁾

Study Procedures	Visit	V1 (Screening)	V2 (Baseline)	V3	V4	V5	V6	V7	V8 / EoS ⁽²⁾	V9 Run-out (Safety F-up) ⁽¹³⁾
	Week	-1	0	2	4	6	8	10	12	14
	Day ⁽¹⁾	-7 to 1	(-5 to 1) ±5	15±2	29±2	43±2	57±2	71±2	85±2	99±2
Brief Assessment of Cognition (BAC) Scale		X	X			X			X	X ⁽⁵⁾
Beck Depression Inventory – II (BDI-II)		X	X	X	X	X	X	X	X	X ⁽⁵⁾
Borderline Evaluation of Severity over Time (BEST)		X	X	X	X	X	X	X	X	X ⁽⁵⁾
Borderline Personality Disorder Checklist (BPDCL)		X	X	X	X	X	X	X	X	X ⁽⁵⁾
State-Trait Anxiety Inventory (STAI) ⁽⁶⁾		X	X	X	X	X	X	X	X	X ⁽⁵⁾
State-Trait Anger Expression Inventory 2 (STAXI-2)		X	X	X	X	X	X	X	X	X ⁽⁵⁾
Clinical Global Impression-Severity for Agitation/Aggression (CGI-S A/A)		X	X	X	X	X	X	X	X	X ⁽⁵⁾
Number of visits to healthcare services outside of the trial (primary care, mental health services & ER visits)			X ⁽⁷⁾		X ⁽⁷⁾		X ⁽⁷⁾		X ⁽⁷⁾	X ⁽⁵⁾
Safety Assessments										
Adverse events			X	X	X	X	X	X	X	X
Vital signs ⁽⁸⁾		X	X	X	X	X	X	X	X	X
Electrocardiogram ⁽⁸⁾		X							X	
Blood sample for laboratory safety assessments⁽⁸⁾										
Hematology		X	X	X	X	X	X	X	X	X ⁽⁵⁾
Biochemistry		X	X	X	X	X	X	X	X	X ⁽⁵⁾
Hep C, Hep B, HIV testing		X								
Blood sample for pharmacokinetic and target engagement⁽⁹⁾										
pK ⁽⁹ⁱ⁾			X		X ⁽⁹ⁱ⁾		X ⁽⁹ⁱ⁾		X	
LSD1-TE			X		X		X		X	
Blood sample for exploratory assessments⁽¹⁰⁾										
Biomarker's analysis			X						X	

Study Procedures	Visit	V1 (Screening)	V2 (Baseline)	V3	V4	V5	V6	V7	V8 / EoS ⁽²⁾	V9 Run-out (Safety F-up) ⁽¹³⁾
	Week	-1	0	2	4	6	8	10	12	14
	Day ⁽¹⁾	-7 to 1	(-5 to 1) ±5	15±2	29±2	43±2	57±2	71±2	85±2	99±2
Genotyping			X							
Investigational Medicinal product (IMP)										
Assess IMP compliance (manual accountability of returned IMP at site)				X	X	X	X	X	X	X ⁽⁵⁾
Dispense IMP ⁽¹¹⁾			X	X	X	X	X	X	X ⁽⁵⁾	

* Screening period will last a week with a window of ± 5 days.

(1) All assessments from a specific visit may be completed over a maximum of two consecutive days. In this case, the first day should be considered as the visit day. The forecasting for visit schedule should take V2 (Baseline) date as the reference. If the date of a visit changes within the allowed window, the following visits will still be scheduled based on V2 (Baseline) date.

(2) After Visit 2, seven visits, every two weeks, are planned until Visit 9. If subjects do not complete all study visits (early termination), then they should complete all the Visit 8/EoS assessments. All subjects are classified as follows:

[figure not shown]
- a. *Completers*: Subjects completing Visit 9.
- b. *Non-completers*: Subjects that received at least one dose of study treatment, but prematurely discontinued the study before completion of Visit 9 for any reason other than withdrawal of the informed consent. These subjects will be asked to complete an End of Study (EoS) Visit as soon as possible after withdrawal. Non-completers will not enter the 2-week subject-blind placebo run-out period.
 - i. If there has been, at least, one week between the last intake of study drug and this EoS visit, no further Safety follow-up visit will be required.
 - ii. If there has been less than one week between the last intake of study drug and EoS visit, subject will be asked to attend to a Safety-follow up visit, two weeks after the last intake of study drug, to perform safety assessments only.
- c. *Non-completers who discontinue the study because they withdraw their consent*: Subjects that received at least one dose of study treatment, but prematurely discontinued from the study before completion of Visit 9 due to withdrawal of informed consent. These subjects, if possible, will be asked to attend to an EoS Visit.
 - i. The visit must be scheduled as soon as possible after withdrawal.
 - ii. If the subject withdraws consent during a visit but agrees to complete the visit, then, the investigator will complete an EoS Visit. All the data collected up to and including this visit will be used in the analysis.
 - iii. If the subject withdraws consent and refuses to complete the EoS Visit, no new information will be collected. However, it is recommended,

[figure not shown]
outside the scope of this study, to perform a safety assessment within 2 weeks after treatment discontinuation.

[figure not shown]
- (3) Informed consent at the Screening visit must be obtained before any study specific procedure.
- (4) Participant eligibility should be documented in a Subject Eligibility Form and submitted to the study medical monitor immediately after Visit 1 for approval before Visit 2.
- (5) Not applicable for non-completers (i.e.: subjects who received at least one dose of study treatment but prematurely discontinue the study before its completion).
- (6) The full State-Trait Anxiety Inventory (STAI) (Forms Y-1 & Y-2) will only be administered at Screening (Visit 1), Baseline (Visit 2) and Visit 8/EoS, whereas Form Y-1 ("state" anxiety) will be administered at all other visits.
- (7) The number of visits to healthcare services outside of the trial (primary care, mental health services & ER visits) will be evaluated 'in the last month' at Baseline and at Visit 4, Visit 6 and Visit 8/EoS.
- (8) Vital signs and electrocardiogram (ECG) should be obtained for a subject in the same manner throughout the study (e.g., obtained from the same arm).
- (9) Blood extractions should take place at the same time of the day and in fasting conditions (first thing in the morning preferably, in order to allow subjects to ingest food before going on with the rest of the study assessments). In case the study visit is scheduled in the afternoon, fasting conditions should last 6-8 hours. Subjects should be instructed to take IMP in fasting conditions.
- (9i) For US Sites ONLY: Cmax will be assessed in a subset of subjects. In these subjects, one extra blood sample for PK assessments will be obtained 1 to 2 hours after IMP intake on Visits 4 and 6 (in addition to the pre-dose sample already scheduled on these visits). Subjects will have to sign a separate specific informed consent form.
- (10) As blood sampling for the exploratory assessments is an integral part of the study, the main Patient Information Sheet covers these analyses
- (11) Study treatment will be dispensed at each study visit from Visit 2 to Visit 8. Each dispensation will consist in a box containing the treatment for 14±2 days. At each visit, the first study drug intake, corresponding to the new treatment box dispensed on that visit, should occur at the clinic.
- (12) ONLY APPLICABLE IN CASE THE SUBJECT IS RECEIVING CONCOMITANT TREATMENT WITH ANTIDEPRESSANTS (i.e., selective serotonin reuptake inhibitors, serotonin-norepinephrine reuptake inhibitors, tricyclics, tetracyclics, and triazolopyridines): A follow-up call will be required approximately 6-8 hours post first IMP administration, as well as at 24 hours and 48 hours to ensure subjects are not experiencing any signs or symptoms of serotonin syndrome. If a subject is experiencing moderate symptoms of serotonin toxicity such as agitation, tachycardia, diaphoresis, and/or hyperthermia, then they will immediately be referred to local emergency services.
- (13) For US Sites ONLY: A subset (i.e., 3-4) of subjects and the PI at each US Site will complete qualitative research regarding their experience with some of the measures used in PORTICO (i.e., BPDCL for subjects & CGI-S A/A and AAPI-CR for clinicians) at Visit 9. Subjects will have to sign a separate specific informed consent form.

[figure not shown]
